7.1.8 Anticipated MRgFUS Treatment Side Effects

Based on previous treatment experience, the above listed side effects have been identified as possible treatment-related complications of ExAblate treatment and procedure. These can be classified into Non-significant and Significant Anticipated Treatment Side Effects based on their medical severity, additional treatment required and long term consequences for the patient. All Treatment Side Effects will be reported in the Case Report Forms for the study and included in the final study analysis.

Non-significant Anticipated Treatment Side Effects of ExAblate treatments are those, which normally resolve without sequelae within 10-14 days of the treatment.

Significant Anticipated Treatment Side Effects of ExAblate are those which may require medical treatment, may have sequelae, and for which time of resolution is not defined. The

Focal MR-Guided Focused Ultrasound Surgery of Intermediate risk, Localized Prostate Lesions

rate of anticipated significant treatment side effects of the ExAblate treatment is unknown, but expected to be infrequent based on prior clinical experience in other organs.

7.2 Adverse Effects and Precautions

The subjects will be counseled concerning what to expect during the procedure and the importance of communicating any problems to the investigator. All device and procedure-related AEs occurring in this study will be recorded in the Case Report Forms. Each AE will be assessed for its probable cause (unrelated to the treatment, device related, procedure related, etc).

7.3 Criteria for Removal from the Study

Early discontinuation from the study may occur for reasons including patient decision, investigator decision, Sponsor decision, protocol compliance and decision to pursue alternative treatments for their tumor. Attempts should be made to complete the final visit study procedures prior to exiting the study. The reason for early discontinuation will be captured on the study Case Report Forms.

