1.3 Rationale for Focal Therapy

Historically, definitive treatment of solid lesions included whole-gland extirpation with radical surgery. For many organ systems, outcome data have supported more selective, organ-sparing, or even ablative therapies, such as breast-conservation surgery and less extensive surgery for melanoma.^{2,3}

Similar trends have been witnessed in urologic oncology. Historically, standard treatment for all solid renal masses was radical nephrectomy. Within the past decade, cancer control following partial nephrectomy has been shown to be equivalent for lesions <4 cm, with the benefit of preserving renal function.^{4,5}

Once established as an accepted treatment for smaller lesions, investigators have subsequently shown similar outcomes following partial and radical nephrectomy in patients with masses ≤ 7 cm.⁶ Likewise, partial cystectomy has proven effective for the treatment of bladder cancer in appropriately selected patients. Prostate lesion ablation may be amenable to organ-sparing, focal treatment. Prostate is a small, easily accessible organ, and many urologists are familiar with performing image-guided procedures in the gland through the rectum, perineum, or urethra. Intuitively, treatment would be required solely at the area of lesion with lesion free margins, limiting collateral damage to normal tissue. While the potential of such therapies makes them attractive, the ramifications of treatment failure bear considerable forethought in the development of focal treatment trials. The issues of patient selection, appropriate targeting of lesions, and impact of focal treatments on outcome with salvage surgical or radiation treatment all deserve consideration. Criteria for follow-up and patient evaluation, as well as indications for repeat treatment, also remain to be standardized.

² Morris AD, Morris RD, Wilson JF, White J, Steinberg S, Okunieff P, Arriagada R, Le MG, Blichert-Toft M, van Dongen JA. Breast-conserving therapy vs mastectomy in early-stage breast cancer: a meta-analysis of 10-year survival. *Cancer J Sci Am* 1997;3:6–12.

³ de Braud F, Khayat D, Kroon BB, Valdagni R, Bruzzi P, Cascinelli N. Malignant melanoma. *Crit Rev Oncol Hematol* 2003;47:35–63.

⁴ Fergany AF, Hafez KS, Novick AC. Long-term results of nephron sparing surgery for localized renal cell carcinoma: 10-year followup. *J Urol* 2000;163:442–445.

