2 OBJECTIVES

2.1 Background

Objective of this trial is to assess safety and effectiveness of ExAblate MRgFUS in the treatment of intermediate risk, localized (organ confined) prostate lesions. Investigators selected for the study will be trained on proper use of the ExAblate system (**Appendix B**).

ExAblate treatment will be implemented as a focal lesion-selective therapy, directed at pre-defined volume(s)/sector(s) in the prostate, identified abnormal by mapping biopsy and multi-parametric MRI), rather than a whole gland or hemi-ablation treatment.

Safety: evaluate incidence and severity of adverse events associated with ExAblate's MRgFUS focal treatment of intermediate risk organ confined prostate lesions. The risk of ExAblate treatment-related incontinence and impotence will also be assessed in this study.

Focal MR-Guided Focused Ultrasound Surgery of Intermediate risk, Localized Prostate Lesions

Effectiveness: determine the lesion control effect of ExAblate's MRgFUS focal treatment of intermediate risk organ-confined prostate lesion (confirmed by IMAGE-guided mapping biopsy results).

The proposed study is to evaluate the preliminary effectiveness and safety of the ExAblate 2100 Prostate System for focal treatment of patients with intermediate risk, localized prostate lesions. Study results will be submitted to FDA as previous discussions with the Agency in a 510k for commercial clearance.

Per FDA requirement, the full 510K submission will be performed following the last treated subject completing their 12-Months visit. Assessments of primary efficacy endpoints will compare the 6-months after ExAblate treatment to Baseline measurements. Safety of ExAblate Prostate treatment will be collected for one year after ExAblate.

It should be noted that all patients will be consented and followed up all the way to 24-Months post treatment.

This study will allow any IMAGE-guided biopsy methodologies (transrectal or transperineal) of 14 cores or more to be used for baseline lesion localization and characterization and for follow-up, but the methodology used should be consistent at all time points for each subject. Successful lesion ablation by ExAblate would result in no residual and/or recurrent lesion at the 6 or 24 month follow-ups. Additional biopsies may be performed between 6- month follow-up visits if judged to be clinically indicated by the investigator.

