2.2 Safety

Safety of ExAblate MRgFUS for focal treatment of intermediate risk organ-confined prostate lesion will be determined by evaluation of incidence and severity of device/treatment related complications from treatment day visit through the 24-month follow-up.

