 - d) At 6-month follow visit patients will be evaluated for physical exam with DRE and urinalysis (culture, if indicated), Multi-parametric MRI, PSA test, concomitant medications, adverse events, and completion of the ICIQ-SF, FACT-P (v4), IPSS, IIEF-15, and SF-12 questionnaires. In addition, all

Focal MR-Guided Focused Ultrasound Surgery of Intermediate risk, Localized Prostate Lesions

patients will undergo a mapping biopsy using the same technique as for screening.

- e) At 9-month follow-up visit, patients will be evaluated for physical exam, with DRE, concomitant medications, AEs and completion of the ICIQ-SF. FACT-P (v4), IPSS, IIEF-15, and SF-12 questionnaires.
- f) At 12-month follow-up visit, patients will be evaluated for physical exam, with a DRE, PSA test, clinical labs for CBC, serum chemistries, urinalysis (with culture if indicated), post-void residual and uroflowmetry if medically indicated based upon the physician's decision, concomitant medications, AEs; and completion of the ICIQ-SF. FACT-P (v4), IPSS, IIEF-15, and SF-12 questionnaires.
- g) At 18-month follow-up visit, patients will be evaluated for physical exam, with a DRE, urinalysis (with culture, if indicated) and PSA, concomitant medications, and AEs and completion of the ICIQ-SF. FACT-P (v4), IPSS, IIEF-15, and SF-12 questionnaires.
- h) At 24-month follow visit, patients will be evaluated for physical exam, with a DRE, PSA test, clinical labs for CBC, serum chemistries, urinalysis (with culture if indicated); post-void residual and uroflowmetry if medically indicated based upon the physician's decision, concomitant medications, AEs; completion of the ICIQ-SF. FACT-P (v4), IPSS, IIEF1-5, and SF-12 questionnaires In addition, all patients will undergo a mapping biopsy using the same technique as used at Baseline and 6-month follow-up.
- i) IMAGE-guided mapping biopsy between the 6-month and the 24-month visits will be done if clinically indicated, based on individual investigator medical opinion.

4.4.1 Early discontinuation of the study may occur for reasons including patient decision, investigator decision, Sponsor decision, decision to pursue alternative treatments for their tumor. Attempts should be made to complete the final visit study procedures prior to exiting the study. The reason for early discontinuation will be captured on the study Case Report Forms.

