4.4.2 Wherever possible, in cases of potential surgical resection of the gland MRgFUS-treated patients, pathology results will be evaluated and compared to the treatment and post treatment data.

5 Study Visit Schedule

See visit schedule on next pages.

**Focal MR-Guided Focused Ultrasound Surgery
of Intermediate risk, Localized Prostate Lesions**

PCa003 Study Schedule				
Visit	Window Allowance	Clinical Office and Lab Tests	Imaging **	Questionnaires
Screening	—	DRE; PSA IMAGE-guided TPBx or TRBx; Clinical labs for CBC, serum chemistries and urinalysis (cultures, if indicated); Physical Exam Concomitant medications	CT, Multi-parametric MRI (E-coil may be used)	FACT-P (v4); ICIQ-SF; IIEF-15 (SHIM); IPSS SF-12
Treatment ***	—	DRE; peripheral oxygen saturation, heart rate, and blood pressure; AEs	MR for planning, treatment and post Tx	Pre-Txt: NRS, FACT-P (v4); ICIQ-SF; IIEF-15 (SHIM); IPSS; SF-12 Post-Txt - NRS
1 week	±3 days	AEs; Physical exam; Concomitant medications		NRS; ICIQ-SF
1 month	± 7 days	AEs; Physical exam with DRE; Proctoscopy and/or post-void residual and Uroflowmetry if indicated; Concomitant medications		ICIQ-SF; IPSS NRS
3 months	± 1 week	AEs; Physical exam; DRE; Concomitant medications		FACT-P (v4); ICIQ-SF; IIEF-15 (SHIM); IPSS; SF-12;
6 months	± 1 month	AEs; Physical exam; DRE; urinalysis (culture, if indicated), PSA; TRBx or TPBx; Concomitant medications	Multi-parametric MRI	FACT-P (v4); ICIQ-SF; IIEF-15 (SHIM); IPSS; SF-12
9 months	±1 month	AEs; Physical exam; DRE; Concomitant medications		FACT-P (v4); ICIQ-SF; IIEF-15 (SHIM); IPSS ; SF-12

**Focal MR-Guided Focused Ultrasound Surgery
of Intermediate risk, Localized Prostate Lesions**

12 months	± 2 month	AEs; Physical exam; DRE; PSA Clinical labs for CBC, serum chemistries and urinalysis (cultures, if indicated); post-void residual and Uroflowmetry if indicated; Concomitant medications		FACT-P (v4); ICIQ-SF; IIEF-15 (SHIM); IPSS; SF-12
18 months	± 2 months	AEs; Physical exam; DRE, urinalysis (Culture, if indicated); PSA Concomitant medications		FACT-P (v4); ICIQ-SF; IIEF-15 (SHIM); IPSS; SF-12
24 months	± 2 months	AEs; Physical exam; DRE; PSA Clinical labs for CBC, serum chemistries and urinalysis (cultures, if indicated); post-void residual and Uroflowmetry if indicated; IMAGE-guided TRBx or TPBx; Concomitant medications		FACT-P (v4); ICIQ-SF; IIEF-15 (SHIM); IPSS ; SF-12

Focal MR-Guided Focused Ultrasound Surgery of Intermediate risk, Localized Prostate Lesions

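### Sections 4.4.1 and 7.3 permit a treated man to leave the study when he chooses other treatment, with no provision for follow-up beyond an attempted final visit

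*Combined protocol and SAP*

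**What the plan says.** Section 7.3, which sets the removal criteria, reads: "Early discontinuation from the study may occur for reasons including patient decision, investigator decision, Sponsor decision, protocol compliance and decision to pursue alternative treatments". Section 4.4.1, under Follow-up: "Early discontinuation of the study may occur for reasons including patient decision, investigator decision, Sponsor decision, decision to pursue alternative treatments for their tumor". The lists match except that only 7.3 includes protocol compliance, a term neither section defines. Both are permissive, both ask for the exit reason on the case report form, and both attach one data safeguard: "Attempts should be made to complete the final visit study procedures prior to exiting the study".

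Four other places bear on the point:

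- Section 2.1, Background: "It should be noted that all patients will be consented and followed up all the way to 24-Months post treatment". The same section says safety is collected for one year and that the 510(k) follows the last subject's 12-month visit.
- Section 2.2, Safety, defines the safety assessment as "incidence and severity of device/treatment related complications from treatment day visit through the 24-month follow-up".
- Section 4.4.2 states, as something to be done where it can be, that "in cases of potential surgical resection of the gland MRgFUS-treated patients, pathology results will be evaluated and compared to the treatment and post treatment data".
- Section 7.4, Adverse Event Reporting, has the investigator evaluate adverse events at each visit. It also says that disease progression leading to another treatment is not reported as an adverse event.

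**The concern.** The device is used in one session, with a second within 12 weeks only if the first was incomplete (section 4.3, item 27). After that there is no study treatment left to stop. Exit therefore has one effect: scheduled data collection ends. Because adverse events are ascertained at visits, ending the visits ends systematic safety ascertainment.

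The permitted reasons are unlikely to be unrelated to outcome. A man who turns to surgery or radiation after focal ablation may well do so because cancer persists or has returned. Investigator and sponsor decisions are made in an open, single-arm study where results are visible. If such men leave, the month 12 and month 24 summaries of adverse events, continence, erectile function and quality of life describe a group selected towards good outcomes. Since progression leading to other treatment is not an adverse event under section 7.4, the exit reason may be its main trace in the data.

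**Working it through.** **Text check.** The plan states no exit rate, dropout allowance, power or missing-data rule, so there is no figure to reproduce. Setting the sections side by side:

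| Question | Where | Answer |
|---|---|---|
| How long are men followed? | 2.1; 4.1 | All patients to 24 months; up to 24 months |
| Over what period is safety assessed? | 2.2; 2.1 | Treatment day to month 24; one year also mentioned |
| Who has the 24-month biopsy? | 4.4, item 6h | All patients |
| May a treated man exit on choosing other treatment, or by investigator or sponsor decision? | 4.4.1; 7.3 | Yes, permitted |
| May he exit for protocol compliance? | 7.3 only | Yes, permitted |
| What is collected at exit? | 4.4.1; 7.3 | Reason, and an attempted final visit |
| What is collected after exit? | none | Nothing, apart from the general wish for resection pathology in 4.4.2 |

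**Person-time lost.** Inputs: 100 men (the minimum in sections 2.1 and 6.2.1), with two assumptions not in the documents: 10 to 30 exits, all at month 9.

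Loss = exits × (horizon − 9) ÷ (100 × horizon).

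- One year: 10 × 3 = 30 and 30 × 3 = 90 of 1,200 person-months, or 2.5% to 7.5%.
- 24 months: 10 × 15 = 150 and 30 × 15 = 450 of 2,400 person-months, or 6.25% to 18.75%.

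The assumed month matters. Exit at month 6 gives 60-180 of 1,200 (5-15%) and 180-540 of 2,400 (7.5-22.5%). Exit at month 12 gives no one-year loss and 120-360 of 2,400 (5-15%).

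**Effect on a late uncommon event.** With m men still observed and an assumed true rate of 2%, the chance of seeing at least one event is 1 − 0.98^m. With no events seen, the one-sided 95% upper limit is 1 − 0.05^(1/m).

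| Exits of 100 | m | Chance of at least one event | Upper limit if none seen |
|---|---|---|---|
| 0 | 100 | 86.7% | 2.95% |
| 10 | 90 | 83.8% | 3.27% |
| 20 | 80 | 80.1% | 3.68% |
| 30 | 70 | 75.7% | 4.19% |

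This table treats leavers as a random subset. With 103 men the results are nearly the same.

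**Bounds on a 24-month proportion.** Assume 80% success among the men observed. With 20 exits, 64 of 80 succeed. Over all 100 treated men the rate lies between 64% (every leaver failed) and 84% (every leaver succeeded). With 10 exits the bounds are 72% and 82%; with 30 they are 56% and 86%. The width equals the exit fraction.

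**The case against.** A planned duration and a list of early-exit reasons normally coexist. The exit text is permissive, section 4.1 speaks of follow-up for at most 24 months, and withdrawal of consent can never be excluded. A final visit is attempted. If that means the month 24 procedures, it brings an examination, PSA, laboratory tests, questionnaires and a biopsy. Section 7.6 asks sites to try hard to contact every subject, with three attempts and a certified letter before a man counts as lost. All of this stands, and it rules out the picture of men being dropped with nothing collected. None of it covers the period after exit.

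A reader might infer several stronger points that the documents do not support:

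- **That the sections flatly contradict each other.** They fit poorly, but a permission does not contradict a planned duration.
- **That resection pathology is cut off.** Section 4.4.2 directly follows the exit rule and still seeks it. Nothing requires exit before surgery. The gap is only that the plan does not say how pathology is obtained once a man has left.
- **That both sections allow removal for non-compliance, or that declining a biopsy means removal.** Only 7.3 names protocol compliance, and the biopsy case is an inference from an undefined term.
- **That the protocol commits itself to collecting salvage complications.** Section 1.3 lists "impact of focal treatments on outcome with salvage surgical or radiation treatment all deserve consideration" among general issues for focal therapy trials.
- **That every leaver is a treatment failure.** The documents give no such data. Likely to include failures is as far as one can go.

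**Conclusion.** The concern holds as a gap that should be closed. Following sections 4.4.1 and 7.3 as written, a treated man can leave the study for reasons tied to his outcome, and no section then provides for his adverse events, function or subsequent treatment to be collected. The likely direction of bias favours the device in the 12- and 24-month safety and functional summaries and in the 24-month biopsy. The one-year data matter most immediately, because the submission follows the last man's 12-month visit. The primary 6-month biopsy result is touched only by exits before it.

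The size is unknown. On the assumed 10 to 30 exits at month 9, the loss is 2.5-7.5% of one-year and 6-19% of 24-month person-time. For that scenario these are upper figures for what the fix could recover, since they count consent withdrawals and losses to follow-up that no wording can prevent. The 24-month figure should not be read as the effect on the one-year safety data. The direction of bias rests on judgement about why men switch, not on data in the documents.

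**What to change.** Amend 4.4.1 and 7.3 to distinguish stopping study procedures from ending follow-up. For treated men:

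- Choosing another treatment, or refusing a procedure, does not by itself end follow-up. Scheduled adverse event, medication and questionnaire contacts continue to month 24 unless consent is withdrawn.
- Record the date and type of the other treatment, and seek resection pathology under 4.4.2 within the scope of consent.
- Tabulate events before and after the switch separately.
- Limit exit by sponsor or investigator decision to stated reasons, and make the two lists of reasons agree.
- Reconcile both sections with section 4.3, item 23. There, a man who has had therapeutic sonications can be classed as a screen failure and exited after a 1-week visit. The plan should say how such men are counted and followed.

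The cost is an amendment to these sections, some extra contacts for switched men, and the work of attributing later events, which the separate tabulation makes manageable. The visits are already on the schedule. Whether consent covers retrieval of outside records and pathology cannot be seen from the documents and should be checked. The change leaves patients and physicians free to choose any other treatment.

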7.4 Adverse Event Reporting

It is the responsibility of the investigator to document all treatment-related and device-related Adverse Events (AE's), which occur during the course of the study. At each visit, the investigator will evaluate AE's. AE's not previously documented in the study will be recorded on the Adverse Event Log within the subject's CRF. The nature of each event, date and time (when appropriate) of onset, outcome, frequency, maximum intensity, action taken, and attribution will be recorded. AEs already documented in the CRF (i.e., at a previous assessment) and designated as 'ongoing', should be reviewed at subsequent visits as necessary. If these have resolved, the documentation in the CRF should be completed including an end date for the event. If an AE increases in frequency or severity during a study period, a new record of the event will be started.

Standard Code of Federal Regulation (CFR) definitions for Serious Adverse Events (SAEs) will be used for evaluation of adverse events.

SAE [§803.3(aa)(1)] is an injury or illness that:

- *causes death*
- *is life threatening, even if temporary in nature;*
- *results in permanent impairment of a body function or permanent damage to a body structure; or*
- *necessitates medical or surgical intervention to preclude permanent impairment of a body function or permanent damage to a body structure.*

All AEs (related or unrelated) meeting the criteria for an SAE require notification of the sponsor and the reviewing IRB as soon as possible, with subsequent completion of additional paperwork provided by the sponsor fully documenting the course of the event, all treatments, and final outcome. Initial reporting of an SAE should be made to the sponsor no later than two (2) working days after the PI learns of the incident.

Focal MR-Guided Focused Ultrasound Surgery of Intermediate risk, Localized Prostate Lesions

Standard Code of Federal Regulation (CFR) definitions for Unanticipated Adverse Device Effects (UADEs) will be used for evaluation of this type of adverse event.

UADE [§812.3(s)] means any serious adverse event on health or safety or any life-threatening problem or death caused by, or associated with, a device, if that effect, problem, or death was not previously identified in nature, severity, or degree of incidence in the investigational plan or application (including a supplementary plan or application), or any other unanticipated serious problem associated with a device that relates to the rights, safety, or welfare of subjects.

Any UADEs will be reported to the Sponsor and to the reviewing IRB as soon as possible. However, in no event must this report be made later than two (2) working days after the PI learns of the incident.

Other common non-study or non-device related, minor health complaints will not be collected as AE's (for example: colds, sprains, headaches). Patients who have a progression of their primary disease or symptoms that lead to an alternative treatment will not be reported as an AE.

